4.1. Description of the Study Design

This is a prospective, **multicenter, open label, randomized Phase III** study of **CPI-613[®] (devimistat) + mFFX** compared to **FFX** in patients with metastatic (Stage IV) adenocarcinoma of the pancreas with age range of 18 to 75 years.

There will be **two study arms**:

1. **Arm 1:** devimistat + mFFX
2. **Arm 2:** FFX

Subjects will be randomized in 1:1 ratio to the experimental treatment or control, using a minimization procedure (Buyse, 2000)²⁰. The minimization algorithm will use the variance method to minimize overall imbalances between the treatment arms with respect to site, performance status (0 vs. 1), and primary tumor location (head vs. body vs. tail of the pancreas).

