9.4.3. Efficacy Analysis

Patients will be allocated to either the control arm or the experimental arm using stochastic minimization, a dynamic treatment allocation procedure that produces good balance with respect to several prognostic factors between the randomized arms (Buyse, 2000)²⁰. When such a procedure is used, the preferred test is a re-randomization test (Simon, 1979)²¹ based on a large number of simulated trials in which patients are re-allocated randomly to the control arm or the experimental arm using the same stochastic minimization, so as to produce an empirical distribution of the test statistic under the null hypothesis. This empirical distribution is used to assign a statistical significance (a re-randomization *P*-value) to the observed test statistic. Arbitrary precision on the re-randomization *P*-value can be obtained by increasing the number of simulated trials. Full details on the re-randomization tests will be provided in the Statistical Analysis Plan. Re-randomization tests will be used as the primary method of analysis, with asymptotic tests used as sensitivity analyses.

The primary analysis will compare the OS observed under the combination therapy devimistat plus mFFX compared to standard care FFX in the ITT population. The comparison will use a re-randomization test based on the log-rank test-statistic, stratified by performance status (0 vs 1) and primary tumor location (head vs. body vs. tail of the pancreas). A stratified log-rank test will be performed as sensitivity analysis. Additional analyses with an unstratified log-rank test and re-randomization test with an unstratified log-rank test-statistic will also be performed. In addition, other sensitivity analyses will be performed, including the censoring of patients who changed treatment at the day the patient received the new treatment and performing all analyses described above on the PP population. The estimation of the survival curves for the 2 treatment groups will be generated using the Kaplan-Meier methodology. More details will be contained in the Statistical Analysis Plan (SAP).

PFS is defined as the duration from the date of randomization to the date of progressive disease or death from any cause. Patients who have neither progressed nor died will be censored at the day of their last radiographic tumor assessment, if available or date of randomization if no post initiation radiographic assessment is available. If death or PD occurs after 2 or more missing

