9.6. Measures to minimize Bias

9.6.1. Enrollment/ Randomization/ Masking Procedures

Subjects will be randomized in 1:1 ratio to the experimental treatment or control, using a minimization procedure. Such a procedure is commonly used in open label cancer trials carried out in a large number of sites, because it produces good balance with respect to several prognostic factors while keeping the treatment allocations unpredictable.

The minimization algorithm will use the variance method to minimize overall imbalances between the treatment arms with respect to site, performance status (0 vs. 1), and primary tumor location (head vs. body vs. tail of the pancreas). A stochastic minimization will be used so that no treatment allocation is deterministic. Note that region is subsumed by site, hence minimization will also tend to balance between the treatment arms with respect to geographical region.

QC procedures will be implemented beginning with the data entry system and data QC checks that will be run on the database will be generated. Any missing data or data anomalies will be communicated to the site(s) for clarification/resolution.

Following written SOPs, the monitors will verify that the clinical trial is conducted, and data are generated, documented (recorded), and reported in compliance with the protocol, GCP, and the applicable regulatory requirements (e.g., Good Laboratory Practice (GLP), Good Manufacturing Practice (GMP)). Data should meet the standard for ALCOA-C

The investigational site will provide direct access without undue restriction to all trial related sites, source data/documents, and reports for the purpose of monitoring and auditing by the sponsor or designee, and inspection by local and regulatory authorities.

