4.1 Randomization

Subjects will be randomized in a 1:1 ratio to the experimental treatment or control via an interactive web response system (IxRS), using a minimization procedure. The minimization algorithm will use the variance method to minimize overall imbalances between the treatment arms with respect to site, and the stratification factors: performance status (0 vs. 1); and, primary tumor location (head vs. body vs. tail of the pancreas). Note that region is subsumed by site, hence minimization will also tend to balance between the treatment arms with respect to geographical region.

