6.1 Re-Randomization Tests

Patients will be allocated to either the control arm or the experimental arm using stochastic minimization, a dynamic treatment allocation procedure that produces good balance with respect to several prognostic factors between the randomized arms (Buyse, 2000). When such a procedure is used, the preferred test is a re-randomization test (Simon, 1979) based on a large number of simulated trials in which patients are re-allocated randomly to the control arm or the experimental arm using the same stochastic minimization, so as to produce an empirical distribution of the test statistic under the null hypothesis. This empirical distribution is used to assign a statistical significance, via an empirically estimated re-randomization p-value, to the observed asymptotic test statistic calculated using the original randomization allocation. Arbitrary precision on the re-randomization p-value can be obtained by increasing the number of simulated trials.

On this study, re-randomization tests will be used as the primary method of analysis, with additional asymptotic tests used as sensitivity analyses. For each analysis where re-randomization tests are used, a total of 10000 simulations will be conducted, in which the seed passed to the stochastic minimization algorithm is randomly generated. Patients will be re-randomized in the same order they were originally randomized. As the stochastic minimization proceeds within each site, the next patient to be randomized is compared on the basis of performance grade and tumor location (i.e., the stratification factors) to the patients previously randomized in that site, and the preferred treatment arm is the one that minimizes the imbalance in strata. The stochastic minimization algorithm is designed so that a patient has an 80% chance of being allocated to the preferred treatment arm, therefore subsequent re-randomizations will introduce new allocations.

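### SAP 6.1 describes re-randomisation within each site, while the protocol and SAP 4.1 describe overall minimisation with site as a factor; the primary test needs one algorithm, taken from the IxRS specification

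*SAP*

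**What the plan says.** Four places describe how patients are allocated, and they agree. Protocol 4.1 reads "The minimization algorithm will use the variance method to minimize overall imbalances between the treatment arms with respect to site", together with performance status and tumour location. Protocol 9.6.1 and SAP 3.2 repeat this, and SAP 4.1 has "The minimization algorithm will use the variance method to minimize overall imbalances between the treatment arms with respect to site, and the stratification factors". Protocol 9.6.1 adds: "Note that region is subsumed by site, hence minimization will also tend to balance between the treatment arms with respect to geographical region".

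Protocol 9.4.3 sets the condition for the primary test: patients are to be "re-allocated randomly to the control arm or the experimental arm using the same stochastic minimization". The opening paragraph of SAP 6.1 repeats that condition.

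The second paragraph of SAP 6.1 then says how the re-randomisation works: "As the stochastic minimization proceeds within each site, the next patient to be randomized is compared" on performance status and tumour location "to the patients previously randomized in that site, and the preferred treatment arm is the one that minimizes the imbalance in strata". It also fixes an 80% probability for the preferred arm, 10,000 re-randomisations, and replay in the order of actual randomisation.

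Re-randomisation is the primary method for OS, PFS and ORR, and is also used for DOR. OS is tested once at one-sided 0.025 and gates the other three.

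**The concern.** A re-randomisation test draws its reference distribution from the allocation procedure. If the simulated allocations follow a different procedure from the real one, the observed statistic is compared with the wrong distribution.

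Read as written, SAP 6.1 makes site a partition: patients at other sites play no part in choosing the preferred arm. In the protocol and SAP 4.1, site is one of three factors whose imbalance is minimised overall. These are different algorithms. Nothing reconciles them, and a programmer who follows SAP 6.1 literally would code the within-site version.

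At stake is the p-value that decides OS and opens the test of PFS, ORR and DOR. If the conflict is noticed only after unblinding, there will be two defensible primary p-values and a choice to make between them.

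**Working it through.** **1. The plan's own figure.** For HR 0.7, one-sided 0.025 and 90% power (SAP 3.3):
- Schoenfeld: 4 × (1.960 + 1.282)² / (ln 0.7)² = 4 × 10.507 / 0.1272 = 330.4, so 331 deaths.
- Freedman: 10.507 × (1.7 / 0.3)² = 10.507 × 32.11 = 337.4, so 338 deaths.

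The plan's 335 lies between them, and power at 335 is 0.904. The event count is not in question and does not depend on the allocation algorithm.

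**2. The two descriptions side by side.**

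| | Protocol 4.1, 9.6.1; SAP 3.2, 4.1 | SAP 6.1 |
|---|---|---|
| Scope | overall imbalance between arms | within each site |
| Role of site | a balancing factor | a partition |
| Compared with | not limited to one site | earlier patients of the same site |
| Balanced on | site, performance status, location | performance status, location |
| Imbalance measure | variance method | not named |
| Preferred-arm probability | not given (protocol 9.6.1: no allocation deterministic) | 80% |
| Ties | not given | not given |

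**3. How far they can diverge.** The documents give 500 or 528 patients and about 78 or 100 sites, which is between 500/100 = 5.0 and 528/78 = 6.8 patients per site. If every site enrols, the first patient at each site has nobody to be compared with under the within-site rule. That is between 78/528 = 15% and 100/500 = 20% of allocations.

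**4. Simulation under the null.** A is overall variance-method minimisation; B is the within-site rule.
- From the documents: 500 patients with 78 sites, 528 with 78, and 528 with 100; 335 deaths; 80% probability; 10,000 re-randomisations per algorithm; log-rank scores stratified by performance status and location.
- Assumed: spread of site sizes, uniform entry over 27 months, prognostic effects, site effects with SD 0, 0.3 or 0.6 on the log hazard, calendar drift 0 or 0.5, equally weighted factor totals, and ties broken 50:50.
- This gives 3 × 3 × 2 = 18 scenarios with 8 datasets each, 144 in all.
- For each dataset, c is the 97.5th percentile of the score under B, and size is the share of scores under A that exceed c.

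| Quantity | A (overall) | B (within site) |
|---|---|---|
| Mean absolute difference in arm totals | about 1.4 | 8.7 to 9.7 |
| Same, within performance status 1 | 1.2 to 1.3 | 6.9 to 7.6 |

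| Allocated by A, tested against B | Result |
|---|---|
| SD of score, B/A, scenario means | 0.977 to 1.012 |
| One-sided size, scenario means | 2.4% to 2.9% |
| One-sided size, single datasets | 1.9% to 3.4% |

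Two smaller runs with 528 patients and 90 sites agree. Twelve datasets with 335 deaths gave 1.7% to 2.9%. Ten datasets with about 380 deaths (an assumption) and 20,000 allocations each gave 2.2% to 3.0%, mean 2.6%, with the SD differing by −4% to +2%.

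**5. How much is noise.** The Monte Carlo error of one dataset's size is √(2 × 0.025 × 0.975 / 10,000) = 0.0022. A one-in-144 tail is z = 2.46, and 2.46 × 0.22 = 0.54 points. Noise alone could therefore stretch the extremes to about 2.0% and 3.0%, and the single-dataset range overstates the true spread.

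The scenario means are firmer. An SD ratio has error about √(1/20,000 + 1/20,000) = 0.010, or 0.010/√8 = 0.0035 for a mean of 8. The lowest mean, 0.977, is (1 − 0.977)/0.0035 = 6.6 such errors below 1. By the normal tail, 1.96 × 0.977 = 1.915 gives 2.8% and 1.96 × 1.012 = 1.984 gives 2.4%, in line with the simulated means.

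**6. On the hazard-ratio scale.** Take the SE of the log HR as 2/√335 = 0.109. The critical HR is exp(−1.96 × 0.109) = 0.807. With the SD 4% too small, the critical z is 1.96 × 0.96 = 1.88 and the critical HR is 0.814. The design HR is 0.70.

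**The case against.** The strongest reply is that SAP 6.1 may be the accurate text. It is the only place that gives operational detail such as the 80% probability, and it can be read as describing the production algorithm. SAP 4.1 itself names site apart from the two stratification factors, and the remark that region is subsumed by site fits either algorithm. If the IxRS ran within site, SAP 6.1 gives the right reference distribution and only the other four places are loosely worded. This stands: the documents do not settle it.

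A reader might therefore infer too much in two ways. One is that the trial is shown to use a wrong reference distribution; the documents show only two incompatible descriptions. The other is that a claimed exactness is lost. The plan never calls the test exact: it calls it preferred, and ties its precision to the number of simulations.

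Three further points carry weight. The rule to re-allocate by the same minimisation, in the same order, is already written. The primary statistic is stratified by performance status and location, which largely removes the effect of the looser balance. The stratified asymptotic test in the ITT population is pre-specified as the first OS sensitivity analysis and reported beside the re-randomisation p-value, so a large discrepancy would be visible.

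None of this removes the conflict. The general rule is contradicted by the paragraph that a programmer would code from, and a sensitivity analysis does not decide the trial.

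**Conclusion.** The contradiction is real and bears on the primary p-value, but its expected size is small. If patients were allocated by overall minimisation and SAP 6.1 is coded as written, the one-sided size stays close to 2.5% on average, with scenario means of 2.4% to 2.9%. In single datasets it ran from roughly 1.7% to 3.4% over all runs, in either direction, with noise contributing to the extremes.

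The conclusion on OS could change only for a p-value near 0.025. Power and the 335 deaths are untouched, and so is the asymptotic stratified test.

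These figures rest on assumed site sizes, site effects, entry pattern, drift, factor weights and tie handling, none of which the documents give. If the IxRS ran within site, there is no error in the test, only in the description of the allocation.

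**What to change.** Before database lock, in this order:

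1. Take the algorithm from the IxRS specification: factors and weights, overall or within-site scope, imbalance measure, the 80% probability, and the handling of ties.
2. State it once, in SAP 4.1, and have SAP 6.1 refer to it. Possible wording: *each simulated allocation replays the algorithm of Section 4.1, patient by patient in the order of actual randomisation*.
3. Correct whichever text is inaccurate: SAP 6.1 if the IxRS minimised overall imbalance, or protocol 4.1 and 9.6.1 and SAP 3.2 and 4.1 if it ran within site. Neither description should be deleted until step 1 is done, because removing the accurate one would create the error.

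The cost is one check against an existing specification and a few sentences of text. Sample size, event count and trial conduct do not change.

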9.2. Trial Design and Statistical Hypotheses

The primary endpoint is overall survival (OS). The primary hypothesis will be tested in the trial, aiming at claiming superior efficacy of the experimental Arm 1 (devimistat + mFFX) over the control Arm 2 (FFX) at the final analysis when the pre-specified number of deaths is reached. The trial is powered to detect an OS hazard ratio equal to 0.7 (a 30% reduction in the risk of death from any cause), assuming a median OS equal to 12 months in the control arm vs. 17.14 months in the experimental arm. Progression-free survival (PFS) will be tested if the primary endpoint reaches significance. Specifically, the hypotheses of interest is that PFS is equal to 6.4 months in the control arm vs. 9.14 months in the experimental arm, i.e. a PFS hazard ratio (HR) equal to 0.7 (a 30% reduction in the risk of tumor progression or death from any cause).

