3.3 Sample Size Justification

A total of 500 patients will be enrolled in this trial across approximately 100 sites in North America, Europe, Asia, and Oceania. This number accounts for ineligible and unevaluable patients, as well as for dropouts.

Dropouts refer to any subject who has been randomized but withdrew for various reasons, including misdiagnosed or exclusion criteria violations.

The sample size calculation is based on the following expected benefits of the experimental treatment (CPI-613 + mFFX) over the control treatment (FFX):

- A 30% reduction in the risk of death from any cause; specifically, median OS is assumed equal to 12 months in the control arm vs. 17.14 months in the experimental arm, i.e., an OS hazard ratio equal to 0.7. For a power of 90% and a one-sided type-I error level of 0.025, 335 deaths need to be observed.
- A 30% reduction in the risk of tumor progression or death from any cause; specifically, median PFS is assumed equal to 6.4 months in the control arm vs. 9.14 months in the experimental arm, i.e., a PFS hazard ratio equal to 0.7. For a power of 90% and a one-sided type-I error level of 0.025, 330 PFS events need to be observed.

4. Data Sources

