4.4 ECG

The 24 patients receiving CPI-613 plus modified FFX (i.e., Arm 1) assigned to the full PK analysis sub-study will also undergo a full ECG analysis. 12-lead ECGs will be recorded at defined intervals from 30 minutes prior to dosing of CPI-613 on cycle 1, day 1 to 6 hours after dosing on day 1. Subjects will be placed in a supine position for at least 10 minutes prior to timepoints for ECG and PK sampling. ECG recordings will be taken immediately prior to PK sample draw at each time point. ECG intervals for this full ECG analysis will be measured at a central ECG laboratory, who will be fully blinded to timepoints and subject identification.

5. General Analysis Definitions

Data will be analyzed using SAS (version 9.4 or higher).

Descriptive statistics will be tabulated as follows:

- Categorical data will be summarized in contingency tables presenting frequencies and percentages.
- Continuous data will be summarized using number of non-missing values (n), mean, standard deviation, median (25th, 75th), minimum, and maximum values.

The baseline tables will be created by treatment arm and overall. Tables containing post-randomization information will be displayed by treatment arm, unless otherwise specified.

Listings with individual values will be provided for all data presented in the tables, where noted. The listings will be presented by identifiers, such as treatment group, center, and patient number.

Confidential

One-sided tests will be used at a significance level equal to 0.025. Two-sided confidence intervals will be computed for a coverage of 0.95.

Time-to-event analyses will be performed using the Kaplan-Meier method. Subjects who have not had the event of interest at the time of the analysis will be censored at the time of the last follow up. Summary statistics will be provided by treatment arm in terms of the number of events, number of censored observations, median, and 95% confidence interval, and survival probabilities at specific time points (such as 1 year, 2 years, etc.). Survival curves will be plotted by treatment arm and compared with a log-rank test stratified by performance status and tumor location. A stratified Cox regression model will be used to estimate the hazard ratio and its 95% CI, as well as to adjust the comparison for baseline covariates.

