5.4 Control Of Type I Error

This study has one primary endpoint of OS. The key secondary efficacy endpoint is PFS.

Testing of these two endpoints will proceed as follows in order to control the overall one-sided type I error of 0.025:

- OS will be tested at a significance level of 0.025. OS will be tested only once at the final analysis.
- PFS will be tested conditionally on the primary endpoint of OS reaching statistical significance, using the significance level of 0.025.
- If OS reaches statistical significance and PFS also reaches statistical significance, then the hierarchical testing procedure will continue to test the rest of the other secondary endpoints in the following order: ORR first, and then DOR, each at a significance level of 0.025.

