This process will generate a total of 10000 treatment allocations, i.e., 10000 variations of `trt01p`. For each of these treatment allocation variants, the pre-specified statistical analysis (e.g., Cochran-Mantel-Haenszel) will be carried out, and the subsequent test statistic estimates will be recorded. The empirical p-value is the frequency, calculated as total number of times out of 10000, that a simulated test statistic is strictly larger (i.e., more extreme) than the asymptotically estimated test statistic on the observed data using the original randomization allocation. For a given analysis, the summary table will display the asymptotic parameter estimate and confidence interval, plus the empirically estimated p-value.

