6.3.1 ORR

ORR is defined as the complete response (CR) rate + partial response (PR) rate. A patient's best response after the start of study treatment will be used for this determination, as assessed by independent, blinded, central review as per RECIST guideline version 1.1 (Eisenhauer, 2009).

In order to define the best overall response, the following rules will be applied:

- CR and PR need to be confirmed no less than 4 weeks apart
- If SD or NON-CR/NON-PD is before 6 weeks after start of study treatment the SD, NON-CR/NON-PD is not taken into account and put to NE in the determination of best overall response.
- Best overall response is defined as the best response after start of study treatment in the following order of assessments: CR, PR (both need to be confirmed), SD or NON-CR/NON-PD (if not too early), PD, NE. For PD there is no confirmation needed.

Among patients in the ITT population, the overall frequency of responders, i.e., patients whose best response after the start of study treatment is CR or PR, will be compared between treatment arms using the Cochran-Mantel-Haenszel (CMH) test, stratified by performance status grade and tumor location.

Subjects who did not receive any study treatment, or who do not have a valid post-treatment efficacy assessment will be classified as not evaluable (NE) or non-responders for response classifications. These subjects will be included in the denominator of the ITT analysis for calculation of response rates.

In SAS, this will be performed with PROC FREQ specifying the cmh option in the table statement. Performance status grade and tumor location, both assessed at baseline, will be included as stratification factors (i.e., controlling for these variables in the table statement); if necessary, a single four-level categorical variable will be derived whose values represent the four distinct patterns of performance status and tumor location.

The significance of the asymptotically estimated CMH statistic will be determined using a re-randomization procedure. The Odds Ratio (OR and confidence limits from the asymptotic test, will be reported.

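### SAP 6.1 does not tie the re-randomization p-value's upper tail to Arm 1 benefit; on the unsigned CMH statistic for ORR it gives a two-sided p judged against one-sided 0.025

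*SAP*

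**What the plan says.** SAP 6.1 makes re-randomization tests the primary method and asymptotic tests sensitivity analyses. For each of 10000 re-allocations, "the pre-specified statistical analysis (e.g., Cochran-Mantel-Haenszel) will be carried out" and the resulting statistic is recorded. The p-value is the frequency "that a simulated test statistic is strictly larger (i.e., more extreme) than the asymptotically estimated test statistic on the observed data".

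The statistic depends on the endpoint:

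- **ORR** (SAP 6.3.1 ORR): "The significance of the asymptotically estimated CMH statistic will be determined using a re-randomization procedure". The statistic comes from PROC FREQ with the cmh option.
- **OS and PFS** (SAP 6.2.1 and 6.3.1 PFS): a stratified Cox model is fitted in PROC PHREG, and the significance of its unnamed statistics is found by re-randomization. Protocol 9.4.3 bases the re-randomization test on a stratified log-rank statistic and does not say whether it is signed or squared.
- **DOR** (SAP 6.3.2): a stratified Cox model with the same unnamed statistics.

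The decision level is set elsewhere. SAP section 5 states "One-sided tests will be used at a significance level equal to 0.025", and SAP 5.4 orders OS, PFS, ORR and DOR "in order to control the overall one-sided type I error of 0.025". Protocol 9.2 states the aim as superiority of Arm 1 over Arm 2.

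**The concern.** A one-sided test needs a statistic whose large values mean benefit. Section 6.1 names the upper tail but not what lies in it, and its gloss, more extreme, gives no direction. Its only example, the CMH statistic for two arms and a binary outcome, is a 1-df chi-square that is large for a difference in either direction. Counting larger chi-squares therefore counts both directions. No passage halves the count, compares it with 0.05, or adds a check on direction.

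At stake for ORR is a result that meets the planned one-sided test but is declared non-significant, which also stops the sequence before DOR. For OS and PFS the text leaves open which statistic decides the trial. The conflict would show only in the results, as a 95% confidence interval that excludes no effect beside a p-value above 0.025. Correcting the rule then would be a post hoc change to a primary analysis method.

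**Working it through.** **Plan's own figure.** Inputs from SAP 3.3: "For a power of 90% and a one-sided type-I error level of 0.025, 335 deaths need to be observed", with HR 0.7 and 1:1 allocation.

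- Schoenfeld: 4 × (1.960 + 1.282)² / (ln 0.7)² = 331 deaths. Freedman's formula gives 338.
- Noncentrality at 335 deaths: −ln(0.7) × √335 / 2 = 3.264. Power is Φ(3.264 − 1.960) = 90.4%.

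The stated 335 is thus consistent with a one-sided 0.025 test.

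**Critical values.** One-sided 0.025 needs z > 1.960. A chi-square count below 0.025 needs chi-square > 5.024, that is |z| > 2.241. The level on the benefit side is then 0.0125, with another 0.0125 on the harm side.

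**ORR (statistic named in the SAP).** The documents give no ORR assumption for this trial. I take 31.6% for control, the published FFX figure in Protocol 2.1.5.2.1, with 250 per arm and an unstratified normal approximation. The smallest significant difference d solves d / √[(2/n) × p(1 − p)] = z, with p = 0.316 + d/2.

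| Patients per arm | z = 1.960 (planned) | z = 2.241 (rule on the CMH) |
|---|---|---|
| 250 (total of 500, SAP 3.3) | 8.4 points | 9.6 points |
| 264 (total of 528, SAP 5.1.1) | 8.2 points | 9.4 points |

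Example: 79/250 against 101/250.

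- Pooled rate 180/500 = 0.36. Standard error √(2/250 × 0.36 × 0.64) = 0.0429. z = 0.088 / 0.0429 = 2.05.
- One-sided p = 0.020, which passes the planned test. Chi-square count p = 0.040, which fails.
- Odds ratio (101 × 171) / (79 × 149) = 1.47. Standard error of its log √(1/101 + 1/149 + 1/79 + 1/171) = 0.187. The 95% CI is 1.02 to 2.12, which excludes 1.

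**OS and PFS, only if a chi-square from PHREG or a squared log-rank is recorded.**

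- OS, 335 deaths, HR 0.7: Φ(3.264 − 2.241) = 84.7%, against 90.4%.
- PFS, 330 events, HR 0.7: noncentrality 3.240. Φ(3.240 − 2.241) = 84.1%, against 90.0%.
- Critical OS HR = exp(−2z/√335): 0.807 at z = 1.960 and 0.783 at z = 2.241. The decision changes for an observed HR between the two.
- Example, observed OS HR 0.80: z = 2.042, one-sided p 0.021, chi-square count p 0.041, 95% CI 0.646 to 0.991.

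A simulation of the re-randomization test itself for OS at HR 0.7 gave 89.7% for a signed statistic and 83.6% for the chi-square count. It used 1,500 trials, 500 patients, 335 deaths and minimization with 80% preference; site sizes and the factor splits were assumed.

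**With a signed statistic oriented to benefit**, the upper-tail share is the planned one-sided p, and nothing is lost.

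**The case against.** The strongest reply is that sidedness is already settled. SAP section 5 and SAP 5.4 prescribe one-sided tests at 0.025, so judging an unhalved two-sided count against 0.025 would breach the SAP's own general rule. On this view section 6.1 is only loosely worded. The intent is indeed clear, and 6.1 does name a tail; what it lacks is orientation. But intent does not give a chi-square a sign. For ORR the SAP names both the statistic and the counting rule, and the two together give a two-sided p.

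Three further points stand. ORR is third in the hierarchy, is tested only after OS and PFS succeed, and has no stated power. The error is conservative for a claim of benefit. The OS and PFS figures depend on a choice that the SAP does not make.

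A reader might infer more than the documents support:

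- *The primary OS test is two-sided at 0.025, so the trial is underpowered.* The SAP does not say that a squared statistic is recorded for OS or PFS. With a signed one oriented to benefit, the planned power holds.
- *Type I error is inflated.* On a chi-square the benefit-side level is 0.0125, below the planned 0.025.
- *Cox in the SAP and log-rank in the Protocol is a second error.* The null distribution is rebuilt for whichever statistic is used, so validity is not threatened. SAP section 5 gives both, the stratified log-rank to compare arms and the stratified Cox model for the hazard ratio. Naming the re-randomized statistic settles the matter.

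**Conclusion.** The point holds as a defect in the definition of the primary p-value. It is established for ORR and conditional for OS and PFS.

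For ORR, the rule as written tests benefit at 0.0125 instead of 0.025 and raises the smallest significant difference by about 1.2 points. That size rests on a 31.6% control rate, equal arms of 250 or 264, and an unstratified approximation; the halving of the level does not depend on those assumptions. For OS and PFS, the established finding is that the deciding statistic and its orientation are not stated. The loss of about 6 points of power follows only if an unsigned statistic is recorded, and is zero otherwise. No false claim of benefit follows from the chi-square reading. This should be fixed before database lock; it does not undermine the design.

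**What to change.** State in SAP 6.1 that the re-randomized statistic is signed, with larger values favouring CPI-613 + mFFX, and that its upper-tail share is compared with 0.025. Name the statistic for each endpoint:

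- OS and PFS: signed stratified log-rank z, as in Protocol 9.4.3.
- ORR: signed root of the stratified CMH statistic.
- DOR: a signed z.

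An equivalent option is to keep the chi-square and require p below 0.05 with the estimate favouring Arm 1. The stratified Cox model can stay for the hazard ratio and its interval.

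The cost is a few sentences in SAP 6.1, 6.2.1 and 6.3 before database lock. Trial conduct, data collection and sample size do not change.
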